#### **8.3.2** Secondary Objective Analyses

Incidence of SARS-CoV-2 will be calculated using Poisson regression with vaccine group as a main effect, and study month as covariates and log person weeks as an offset. Person weeks is defined as the time at risk (in days) divided by seven and rounded up. If assumptions for Poisson regression do not hold, zero-inflated Poisson and Negative Binomial models will be considered instead.

Proportional hazard or logistic regression analyses will be used to assess hazard ratio or relative risk and associated 95% confidence intervals for secondary endpoints such as individual, occupational, and environmental predictors of SARS-CoV-2 infection and of asymptomatic infection versus symptomatic COVID-19 illness. The choice to use PH or logistic model will depend on the specific secondary outcome being identified. If PH models are used, time-varying covariates will be used as available. Multivariable models will be adjusted for potential confounders.

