5.5.2 Active Surveillance for Acute Illness

Surveillance for acute illness will be conducted throughout the study period.

Participants will be prompted to begin active surveillance immediately following their enrollment visit. The participant dashboard will contain video instructions reminding them about how to store the RATs, self-collect the nasal specimen, interpret the results on the cassette (Table 2. Interpretation of results based on status of first day of testing), and submit their results. A contact number and email address will be provided to call, text, or email with questions or to talk to a study staff member.

To determine acute illness, participants will be asked if they developed subjective COVID-like illness (CLI) symptoms since the day of their last scheduled surveillance. The primary means for detecting acute illnesses during the study period will be through a Weekly Active Surveillance system (conducted in English) using a text message platform. The online surveys for weekly surveillance, specimen collection and self-testing, and illness assessments, are outlined in Appendix G1: Surveillance and Illness Messaging Surveys. These are also illustrated in Appendix G2. Messaging and Survey Flow Diagram. Procedures for capturing weekly surveillance will include SMS response, a link to a response-specific online survey, spontaneous reporting of CLI symptoms by participants clicking a button on their participant dashboard, or in special circumstances, an email or phone call may be used as well. Each week, all participants will be contacted to ascertain the development of symptoms and be reminded to collect a weekly specimen and upload the photo of the RAT result (Appendix G1: Surveillance and Illness Messaging Surveys). Participants will have an assigned routine day for communication and specimen collection and self-testing.

CLI will be defined as an episode that includes at least one subjective (i.e. participant-reported) CLI symptoms. Specifically, the participant is asked if they have experienced one or more of the following CLI symptoms in the past 7 days:

- o Fever
- o Chills
- Malaise

- Fatigue
- o Headache
- Cough
- Shortness of breath
- Sore throat
- Runny nose or nasal congestion
- Nausea or vomiting
- Diarrhea
- Muscle or body aches
- Change in smell or taste

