# **Efficacy**

#### Time at Risk

- Beginning of time at risk starts with the first active surveillance contact
- End of time at risk is illness onset with rapid test confirmed SARS-Co-v2 virus infection or the last submitted response to study surveillance.
  - o Illness onset is defined for participants with an illness as the earlier of the first positive swab collection (excluding false positives) and the date of reported symptom start.
- Duration of time at risk in days is defined as: End of time at risk beginning of time at risk + 1.
- We will assess the need to statistically adjust for time since last infection or time since last vaccination as 2 separate potential covariates

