If models for a single month do not meet the proportional hazard assumption, the Andersen and Gill counting method will be used to allow for weekly circulation as a covariate. If a model still does not meet the assumption the proportional hazards assumption after the inclusion of weekly circulation as a covariate, the Prentice, Williams, and Peterson total time model will be used with season as a strata and circulation as a covariate, allowing for circulation to vary. Participants who do not experience a SARS-CoV-2 case prior to the discontinuation of the study will be right censored at their last response to weekly surveillance contacts.

The relative vaccine efficacy against SARS-CoV-2 illness for NVX boosted participants versus mRNA boosted participants will be calculated with the mITT population using time at risk with the following null and alternative hypotheses for the objective comparing NVX vs mRNA:

$$H_0$$
: rVE < -50 and  $H_a$ : rVE $\geq$  -50

Here rVE is estimated with the same analytic approach described for the VE, however the Cox proportional hazard models will have NVX arm versus the Pfizer arm as the main effect. The primary objective will be achieved if the lower limit of the one-sided 95% confidence interval of rVE estimate exceeds -50 between NVX and Pfizer mRNA vaccine groups, adjusting for potential confounders or differences in baseline groups.

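### Rounding each participant's person-weeks up biases the secondary Poisson incidence rates downward by about 2–4%; rate ratios and the primary Cox results are essentially unaffected

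*SAP*

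**What the plan says.** SAP 8.3.2 estimates the incidence of SARS-CoV-2 by Poisson regression with vaccine group as the main effect and "study month as covariates and log person weeks as an offset". The unit is then fixed: "Person weeks is defined as the time at risk (in days) divided by seven and rounded up". Protocol 6.1.4 has the same definition.

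The days that enter this formula are defined in SAP 7.5 (Time at Risk):

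- Start: "Beginning of time at risk starts with the first active surveillance contact".
- End: "End of time at risk is illness onset with rapid test confirmed SARS-Co-v2 virus infection or the last submitted response to study surveillance".
- Duration: "End of time at risk beginning of time at risk + 1". The minus sign is lost in the available text; it reads as end minus beginning plus 1.

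SAP 8.3.1 adds that participants without a case are "right censored at their last response to weekly surveillance contacts". On the spacing of contacts, protocol 5.5.2 says: "Participants will have an assigned routine day for communication and specimen collection and self-testing". Protocol 5.6.1 asks that the sample ideally be taken within 24 hours of the weekly text.

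Neither document gives a reason for rounding up or says how study month is defined.

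**The concern.** A round-up rule can lengthen person-time but never shorten it, so the error does not average out and does not shrink with sample size. Here it also meets an unfavourable pattern. With an inclusive day count and contacts seven days apart, an on-schedule non-case has exactly one day more than a whole number of weeks, and that single day is charged as a full week. At the planning event probabilities (10.08% in protocol 6.1.1, 13.44% in SAP 4.1), most participants are non-cases.

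What is at stake is the absolute incidence in each arm, which is what this model is there to report. The exact number of days is already derived under SAP 7.5, so the rounding discards information that the trial has.

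**Working it through.** **Reproducing the plan's own rate figures.** The documents state no incidence result and no rounding effect. The nearest figures are the planning rates over 24 weeks (168 days).

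- SAP 4.1: 80/100,000 × 168 = 0.1344; −ln(1 − 0.1344) = 0.14433. Both match.
- Protocol 6.1.1: 60/100,000 × 168 = 0.1008; −ln(1 − 0.1008) = 0.10625. Both match.

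**Days added for one non-case.** Let k be the number of weeks between the first contact and the contact last answered, and d the delay of that last response in days (0 to 6).

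- Days at risk: t = 7k + 1 + d.
- Days counted: 7 × ceil(t/7) = 7(k + 1).
- Days added: 7(k + 1) − (7k + 1 + d) = 6 − d.

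| Contacts (k + 1) | Delay d | Days at risk | Days counted | Inflation |
|---|---|---|---|---|
| 24 | 0 | 162 | 168 | +3.7% |
| 24 | 1 | 163 | 168 | +3.1% |
| 24 | 3 | 165 | 168 | +1.8% |
| 24 | 6 | 168 | 168 | 0% |
| 25 | 0 | 169 | 175 | +3.6% |

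Early dropouts gain the same days on a shorter base: k = 4 and d = 0 gives 29 days counted as 35, or +21%.

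**Effect on the arm-level rate.** This was simulated with constant hazards, 24 weekly contacts, onset on any day and the planned 15% attrition (dropouts stopping at a random earlier contact). Rates are per 100,000 person-days at a true rate of 80.

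| Delay of last response | Exact days | Rounded up | Rate too low by |
|---|---|---|---|
| Same day | 80.31 | 77.19 | 3.9% |
| 0–1 day | 79.73 | 76.88 | 3.6% |
| 0–3 days | 80.08 | 77.70 | 3.0% |
| 0–6 days, evenly spread | 79.95 | 78.31 | 2.1% |

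For same-day responses, the protocol's planning rates of 60 and 48 behave alike: 60.09 becomes 57.76 and 48.00 becomes 46.14. Cases gain about 3 days on average. The same-day bias exceeds the 1 − 162/168 = 3.6% of a full-length non-case because of the dropouts.

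**Effect on the rate ratio.** With same-day responses it is 0.4986 exact against 0.4987 rounded (true ratio 0.5), and 0.7988 against 0.7989 (true ratio 0.8). Over all delay patterns the largest change is 0.0003.

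**Conditional scenario: rounding after a split by month.** Study month changes within a person over 24 weeks, so an analyst may split person-time at month boundaries and apply the rule to each piece. For 162 days starting on 1 December 2023, the calendar-month pieces are 31, 31, 29, 31, 30 and 10 days. They round to 5 + 5 + 5 + 5 + 5 + 2 = 27 weeks = 189 days, and 189/162 = 1.167. Over every start date from 1 November 2023 to 29 February 2024, equally weighted (an assumption), the inflation runs from 12% to 21% with mean 16.2%, so the rate is 1 − 1/1.162 = 13.9% too low on average. With 28-day months the pieces are five of 28 days and one of 22, which give 24 weeks: +3.7%, as without a split.

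**The case against.** **No stated inference moves.** Primary VE and rVE come from Cox models on time at risk in days, and rate ratios do not change. The bias is also small beside sampling error: with the protocol's expected 55 vaccinated and 30 unvaccinated cases at a VE of 50%, the 95% half-width on the log-rate scale is about 1.96/√55 = 0.26 and 1.96/√30 = 0.36. All of this stands. It limits the importance of the point but does not justify a one-directional error that costs nothing to remove.

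**Twenty-four contacts may be meant as 24 weeks.** Each contact asks about the past 7 days, surveillance is planned for 24 weeks, and 162 days rounded up is 168. SAP 1.2.1 also starts the endpoint clock at the later of enrolment or the start of active surveillance, without naming the first weekly contact. The rule could be a deliberate count of surveillance weeks. But it is applied to time at risk, which SAP 7.5 starts at the first contact, so the added days are not observed risk time under the plan's own definition.

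**Six days is an upper bound.** It needs a last response on the same weekday as the first contact. Responses can come late, spontaneously through the dashboard, or with the illness tests on Days 1 and 3. This stands; hence a range of 2–4% rather than a single figure.

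**Two stronger readings are not supported.** A reader might infer that incidence will be about 14% too low. That requires both a calendar-month split and rounding of each piece. The SAP lists study month only as a covariate, and SAP 7.5 defines time at risk once per participant. A reader might also infer that the fallback ("zero-inflated Poisson and Negative Binomial models will be considered instead") is wrong because time at risk ends at a confirmed illness, leaving at most one event per person. The documents do not settle this: protocol 5.5.2 recognises a new illness more than 90 days after the last, which fits within 24 weeks; protocol 4.2 objective 5 studies re-infection in the study window; and the Andersen-Gill approach in SAP 8.3.1 can accommodate repeat events.

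**Conclusion.** The point holds for the absolute incidence rates of the secondary Poisson model, and only for them. The direction follows from the definitions alone. The size is about 2–4% too low in every arm: 3.6–3.9% if last responses fall on the assigned day or the day after, and about 2% if they are spread evenly over the week. These figures assume 24 weekly contacts, 15% attrition and constant hazards.

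The 12–21% inflation of person-time is a scenario. It shows why study month and the order of splitting and rounding should be stated, but it is not a finding about what the plan will do. This is a worthwhile correction of low consequence, and it gives no ground to question the primary conclusions or the fallback models.

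**What to change.** In SAP 8.3.2 and protocol 6.1.4, define person-weeks as days at risk divided by seven without rounding, so that the offset is log(days at risk / 7), with days as in SAP 7.5. In the same place, say what study month means (calendar month or a fixed block of days since start) and, if person-time is split by it, that exact days are split at the boundaries with no rounding of the pieces.

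The cost is a sentence or two in each document. It needs no new data, no change to follow-up and no change to the primary analysis.

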# 8.3.3 Sensitivity analysis

In addition to the above specified primary analysis, the following analyses will be conducted as sensitivity analyses:

- The primary efficacy analysis will be repeated using the per protocol population.
- The primary efficacy analysis will be repeated using mITT population who complete ≥20% of surveillance each season.

# 9. SAFETY ANALYSES

Since all study vaccines are licensed for use in participants meeting the eligibility criteria and safety and tolerability of each vaccine have been established in prior studies, data on reactogenicity events will be solicited in a separate reactogenicity substudy. This substudy has separate protocol and statistical analysis plan (SAP) documents (Refer to Appendix S2 and the Post-Vaccination Substudy Protocol).

